It is mandatory that patients agree to undergo two research biopsies, which will be analyzed to evaluate how this experimental approach changes the genomic/transcriptomic landscape of the tumor and the tumor immune infiltrate (exemption from the second biopsy may be considered if after performance of the first biopsy it is felt that a subsequent biopsy is not reasonably safe for the patient). Archival tumor tissue and serial peripheral blood collections will also be analyzed for potential biologic correlates of immune activation and efficacy derived from the combination therapy.

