9.3 Schedule of Events

- Patients will initiate treatment with durvalumab on Week 1, Day 1. The required evaluations and laboratory tests (detailed in **Section 10**) can be performed up to 7 days prior to initiation of treatment. It is unnecessary to repeat laboratory tests if the screening assessments of the same tests were performed within 7 days prior to first dose of therapy. Durvalumab 1500 mg IV

approximately every 4 weeks will be administered (adjustment to the dose may be necessary for patients weighing <30 kg). All other Week 1 evaluations (detailed in **Section 10**) may be performed up to 3 days prior to initiation of study treatment.

- In Cycle 1/Week 3, Thyrogen 0.9 mg IM will be administered on two consecutive calendar days followed by 100 mCi (+/- 10 mCi) RAI the next calendar day (these agents will be administered in clinic). The laboratory tests detailed in **Section 10** are to be drawn prior to the first Thyrogen injection.
- Research tumor biopsy: If after performance of the first research biopsy the investigator judges that it is safe to proceed with a second research biopsy, it is preferred that the procedure be performed during Cycle 2, Week 3 or 4 (though alternate timing for this second biopsy during Cycle 2 or later is allowed per investigator discretion or for safety reasons related to RAI administration). Biopsy of the same tumor that was sampled previously is preferred, but not required. Radiologic guidance (CT, MRI or ultrasound guided) approaches and obtaining multiple cores to ensure sufficient biopsy material (at least 3 cores preferred) are allowed as long as it is considered safe for the patient (image-guided biopsies will be performed by a radiology physician with the appropriate expertise).
- DLT monitoring and evaluations (including research blood collections) are to be conducted according to the schedule detailed in **Section 10**. Guidelines for holding durvalumab will be performed as outlined in **Section 11** and **Appendix 1**.

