Rationale: We hypothesize that disruption of the PD-1/PD-L1 axis with durvalumab in combination with rhTSH-prepared RAI therapy will alter peripheral blood immune populations. Additionally, T cell receptor repertoire may be analyzed.

Approach: (These studies will be conducted in collaboration with the MSK immune monitoring core facility.) At the time points indicated in **Section 10**, peripheral blood samples will be collected: 4 CPT tubes (BD, 8-ml capacity, total blood volume collected ~32 ml for PBMC purification for flow cytometric analysis) and 1 PAXgene tube (BD order #762165 or equivalent) (for purification of RNA/DNA for TCR analysis). Changes to these methods may be adapted depending upon the most recent, generally accepted protocols. Flow cytometry will be used to evaluate changes in T cell subsets at different time points. Alternative approaches to this analysis may be pursued depending upon the availability of new technologies, platforms, or approaches. Specifically, assays investigating the immunogenicity of tumoral antigens in *ex vivo* assays utilizing these collected PBMCs may be of value and will be performed to identify potential neoantigens or self antigens that are critical for mediating therapeutic efficacy.

Exploratory Objective #2: To investigate changes in cell free DNA (cfDNA) that occur with durvalumab and rhTSH-prepared RAI.

Rationale: We hypothesize that rhTSH-prepared RAI therapy will enhance expression and release of thyroid-specific antigens/neoantigens critical for augmenting immunotherapeutic responses to PD-L1 targeting with durvalumab. Here, we propose using tumor cfDNA as a surrogate marker of tumor lysis and antigen release.

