- o: Peripheral blood samples will be collected for peripheral T cell analysis as well as cfDNA analysis. For peripheral T cells, blood will be collected in 4 CPT tubes (BD, 8-ml capacity, total blood volume collected~32 ml for PBMC purification for flow cytometric analysis) and 1 PAXgene tube (BD order #762165 or equivalent) (for purification of RNA/DNA for TCR analysis). For cfDNA analysis, blood will be collected in 10-ml Cell-Free DNA BCT tubes (STRECK). These blood samples (peripheral T cells and cfDNA) will be collected Cycle 1/Week 1 (prior to durvalumab). In Cycle 1/Week 3 or 4, only the cfDNA sample will be drawn at various time points: on the day of first Thyrogen injection (but prior to Thyrogen injection) and on the day of RAI administration (but prior to RAI ingestion).
- p: Research blood collection (for peripheral T cell analysis and cfDNA analysis) after Cycle 1 will be conducted on Week 1 of Cycles 2, 3, and 4 (preferably prior to durvalumab administration, if possible), as well as Off Study. Cycle 2 cfDNA collection does not have to be performed if the Principle Investigator decides that it is redundant given the cfDNA collections performed for **footnote o**.
- q: Confirm availability of archival tumor tissue (if tissue is not already available at MSK, physical receipt of tissue is not required for study enrollment or initiation).
- r: TSH, thyroglobulin (TG), and antibody serologies for TG, thyroperoxidase (TPO), and TSH receptor (TSHR) will be drawn Cycle 1/Week 1 (prior to durvalumab). In Cycle 1/Week 3, TSH and TG will be drawn at various time points: on the day of first Thyrogen injection (but prior to Thyrogen injection) and on the day of RAI administration (but prior to RAI ingestion). Subsequently, TSH and TG will be drawn on Week 1 of every cycle. Additionally, antibody serologies for TG, TPO, TSHR will be required to be drawn on Week 1 of every even numbered cycle, up to and including Cycle 6.
- s: EKG will be performed in triplicate. Repeat the EKG in Cycle 1 (Week 3)(only 1 EKG required at that time point).
- t: If Cycle 1 Week 1 labs fall below screening requirements, the patient can start treatment at the discretion of the treating investigator if safety is not compromised.
- u: Week 1 evaluations/tests and research collections during Cycles 2 and beyond may be performed up to 3 days prior to the patient being treated.

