11.1 TOXICITIES/SIDE EFFECTS

For adverse events (AEs) that are considered related to administration of durvalumab, the following may be applied:

- Following the first dose of durvalumab, subsequent administration of durvalumab can be modified based on toxicities observed (see **Appendix 1**). Dose reductions are not permitted.
- Treat each of the toxicities with maximum supportive care (including holding the agent suspected of causing the toxicity where required).
- If the symptoms promptly resolve with supportive care, consideration should be given to continuing the same dose of durvalumab along with appropriate continuing supportive care according to guidelines outlined in **Appendix 1**.
- If modification of durvalumab treatment is required prior to the administration of RAI, delay in giving Thyrogen and RAI therapy prior to the second dose of durvalumab is allowed if the patient remains on study.
- In addition, there are certain circumstances in which durvalumab should be permanently discontinued.
- Cycle 2 and 3 doses of durvalumab will not be held for hematologic cytopenias (leukopenia, anemia, neutropenia, thrombocytopenia), which can occur following RAI therapy.
- Re-starting of durvalumab administration after holding therapy for toxicity can be done at the investigator's discretion as long as criteria in **Appendix 1** are fulfilled. The week that durvalumab is re-started will then be considered to be Week 1. Subsequent treatments and evaluations can then be scheduled accordingly.

Based on the mechanism of action of durvalumab leading to T-cell activation and proliferation, there is the possibility of observing immune related Adverse Events (irAEs) during the conduct of this study. Potential irAEs include immune-mediated enterocolitis, dermatitis, hepatitis, and endocrinopathies. Subjects should be monitored for signs and symptoms of irAEs. In the absence of an alternate etiology (e.g., infection or PD) signs or symptoms of enterocolitis, dermatitis, hepatitis, and endocrinopathy should be considered to be immune-related.

Dose modification recommendations and toxicity management guidelines for immune-mediated reactions, for infusion-related reactions, and for non-immune-mediated reactions related to durvalumab are detailed in Appendix 1. In addition, management guidelines for adverse events of special interest (AESIs) are detailed in **Appendix 1**. All toxicities will be graded according to NCI CTCAE v4.0.

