Intratumor heterogeneity analysis: Recently we have developed a technique to characterize the intratumor genetic heterogeneity of tumors based on sequencing data³². Using copy number and mutational data, our computational pipeline infers subclonal populations in tumors. Here, we propose to characterize the evolution of tumors under the selective pressure of rhTSH-stimulated RAI and durvalumab treatment, and examine subclonal expansions that are associated with an immune escape phenotype, by comparing the subclonal architecture of pre- and post-treatment samples.

PBMCs: In addition to the research biopsies, peripheral blood samples will be collected serially for flow cytometry to evaluate changes in T cell subsets at different time points of therapy.

Biostatistical analysis: Proportions of T cell subsets will be summarized at each time point and plotted to reveal any trend.

cfDNA: Collected cfDNA will be analyzed to detect and quantify total cfDNA and the amounts of tumor driver oncogenes (BRAF mutations, RAS mutations, etc...) or other gene mutations present

as appropriate. *Biostatistical analysis*: Changes in these parameters that occur with therapy will be analyzed by graphical method.

Accrual to the trial is anticipated to be approximately 1 patient per month.

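### T cell subsets are summarised only as proportions, after an RAI dose that can lower white cells; absolute counts should be shown beside them

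*Combined protocol and SAP*

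**What the plan says.** **Analysis.** Under PBMCs, Section 14.0 gives the whole plan: "Proportions of T cell subsets will be summarized at each time point and plotted to reveal any trend". Section 9.5 adds "Flow cytometry will be used to evaluate changes in T cell subsets at different time points" and describes no method for counting cells. Section 1.0 states the purpose: "serial peripheral blood collections will also be analyzed for potential biologic correlates of immune activation", and of efficacy.

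**Sampling.** Section 10.1, footnote o, places the first T cell sample in Cycle 1/Week 1, before durvalumab. Around Thyrogen and RAI it restricts the draws: "In Cycle 1/Week 3 or 4, only the cfDNA sample will be drawn at various time points". Under footnote p, later collections "will be conducted on Week 1 of Cycles 2, 3, and 4", with one more off study. On RAI, Section 9.3 says "In Cycle 1/Week 3, Thyrogen 0.9 mg IM will be administered on two consecutive calendar days", and RAI follows on the next day.

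**White cells.** Section 11.1 says that the Cycle 2 and 3 durvalumab doses are not held for "hematologic cytopenias (leukopenia, anemia, neutropenia, thrombocytopenia), which can occur following RAI therapy". Section 9.4 does not count a Grade 3 low white cell count within 30 days of RAI as a DLT. Its general exclusions, not tied to RAI, also cover Grade 3 or 4 lymphopenia.

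**Data at hand.** Lymphocytes are in the hematology panel (Section 10.1, Table 1). The panel is scheduled at Cycle 1 Weeks 1 and 3, at Week 1 of each later cycle, and off study. No section combines that count with the flow cytometry results.

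**The concern.** A proportion has a numerator and a denominator, and RAI may change both. If a subset's share of T cells rises between Cycle 1 and Cycle 2, the subset may have expanded, or the other T cells may have fallen further than it did. The planned plot looks the same in either case. The trial has a single arm, so no group without RAI is available to show the difference.

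The blood is collected to look for correlates of immune activation. What is at stake is whether a trend in that plot is read as expansion when it is depletion, or missed because depletion offsets it. The first T cell interval also spans both the first durvalumab dose and RAI, so a change across it cannot be assigned to either agent.

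**Working it through.** The plan states no sample size, effect or precision for this analysis, so there is no figure to reproduce. The check is on the order of sampling and on how proportions behave.

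**1. Order of sampling, nominal schedule.** Week 3 runs from Day 15 to Day 21. Two Thyrogen days come first, so RAI falls on Day 17 at the earliest and Day 21 at the latest. Cycle 2 Week 1 starts on Day 29.
- Interval from RAI to a Day 29 draw: 29 − 21 = 8 days to 29 − 17 = 12 days.
- Footnote u lets Cycle 2 and later collections be taken up to 3 days early, so the shortest interval is 26 − 21 = 5 days.
- The nominal interval is therefore about 5 to 12 days. Footnotes i and o and the rescheduling note in Section 10.1 can move it further.
- All later scheduled draws come after this one, so for a patient who receives RAI on this schedule every T cell sample after baseline follows it.

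**2. Formula.** Let f be the subset's baseline share of T cells, s the fraction of the subset lost, and r the fraction of all other T cells lost, with no activation or expansion. Then

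share after = f(1 − s) / [f(1 − s) + (1 − f)(1 − r)].

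The share rises whenever r exceeds s, falls whenever s exceeds r, and is unchanged when they are equal.

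**3. Numbers.** All values of f, s and r are assumptions.
- Selective loss, f = 0.30, s = 0.30, r = 0.50: 0.21 / (0.21 + 0.35) = 0.21 / 0.56 = 37.5%. The share rises by a quarter (0.375 / 0.30 = 1.25) while the count falls by 30%.
- Equal loss, f = 0.30, s = r = 0.30: 0.21 / (0.21 + 0.49) = 30%. There is no artefact.
- Opposite pattern, f = 0.30, s = 0.50, r = 0.30: 0.15 / (0.15 + 0.49) = 23.4%. A fall of this kind could offset a real expansion.
- Range with no loss in the subset: at f = 0.50, r = 0.20 the share is 0.50 / 0.90 = 55.6%, a relative rise of 11%. At f = 0.10, r = 0.50 it is 0.10 / 0.55 = 18.2%, a relative rise of 82%. The true change in count is zero in both cases.

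**4. What the absolute scale shows.** Take baseline T cells as 1. In the selective-loss case total T cells fall to 0.56, so the subset goes from 1 × 0.30 = 0.30 to 0.56 × 0.375 = 0.21, a ratio of 0.70. The proportion alone shows a rise; the count shows the loss.

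**The case against.** The case against giving this much weight is substantial.

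- **Selective loss is not shown.** The documents do not say that RAI depletes T cell subsets unequally, and equal loss does no harm. Section 11.1 says cytopenias can occur. A reader might infer that the protocol expects lymphopenia after RAI, but lymphopenia is not named there, nor in the list of toxicities excluded within 30 days of RAI. Neutropenia would not distort fractions within purified mononuclear cells. This stands: the artefact is possible, and its size and direction are unknown.
- **Reach.** A reader might infer that every post-RAI sample is distorted, or that the conclusion would change sign. The documents support neither. On the nominal schedule the Cycle 3 and 4 draws come 28 and 56 days after the Cycle 2 draw, and nothing shows how long any depletion lasts. A change of sign depends entirely on the loss rates assumed.
- **Aim.** A reader might infer that the plan must separate durvalumab from RAI in T cells. The first peripheral blood objective in Section 9.5 concerns changes with the combination, and its hypothesis has no direction. Within the peripheral blood analyses, the RAI-augmentation rationale belongs to the cfDNA objective, which does have draws before Thyrogen and before RAI.
- **Recoverability.** Section 9.5 allows alternative approaches, and the lymphocyte counts will exist, so counts could be derived later. This limits the consequence. It does not argue against naming the better summary now, before the data are seen.

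**Conclusion.** The point holds as a modest improvement to an exploratory analysis. Section 14.0 specifies proportions only, on samples that after baseline all follow a dose with acknowledged leukopenia, and a proportion cannot distinguish expansion of a subset from greater loss of other cells. Under the assumed losses of 30% and 50%, a subset at 30% reads 37.5% while its count falls by 30%. That illustrates the mechanism and does not estimate what this trial will show. It rests on selective depletion, which the documents neither establish nor rule out.

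The primary and secondary objectives are untouched. The missing pre-RAI T cell sample limits how results may be described; it is not a failure to meet the stated T cell objective.

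**What to change.** In Section 14.0, under PBMCs:

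1. State the denominator of each proportion.
2. Summarise and plot each subset as an absolute count beside its proportion: lymphocyte count from the same or nearest visit × T cell share of lymphocytes × subset share of T cells. If a proportion is defined on another denominator, adapt the chain; multiplying a share of T cells directly by the lymphocyte count would be wrong.
3. Show days since RAI for every sample.
4. Say that changes are those of the combination and will not be attributed to durvalumab or RAI alone.

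The cost is analysis wording. The lymphocyte count is already scheduled at the T cell visits. The T cell share should come from the same flow cytometry run, provided the panel identifies total lymphocytes, which the laboratory should confirm. No extra blood or visit is needed.

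Drawing T cell tubes at the existing pre-Thyrogen cfDNA draw is optional and not part of this fix. It would show the change under durvalumab before RAI, at the price of about 32 ml more blood and one PAXgene tube per patient, plus processing for up to 11 samples.

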9.1 TREATMENT/INTERVENTION PLAN

9.2 Concomitant Medications

The following medications are considered exclusionary during the study.

1. Any investigational anticancer therapy.
2. Any concurrent chemotherapy, radiotherapy (except palliative radiotherapy), immunotherapy, biologic or hormonal therapy for cancer treatment, other than TSH suppressive therapy and/or bisphosphonates and/or denosumab.
3. Immunosuppressive medications including, but not limited to, systemic corticosteroids at doses exceeding 10 mg/day of prednisone or equivalent, methotrexate, azathioprine, and TNF- α blockers. Use of immunosuppressive medications for the management of investigational product-related AEs or in subjects with contrast allergies is acceptable. In addition, use of inhaled and intranasal corticosteroids is permitted. A temporary period of steroids will be allowed for different indications, at the discretion of the principal investigator (e.g., chronic obstructive pulmonary disease, radiation, nausea, etc).
4. Live attenuated vaccines within 30 days of durvalumab dosing (i.e., 30 days prior to the first dose, during treatment with durvalumab and for 30 days post discontinuation of durvalumab). Inactivated vaccines, such as the injectable influenza vaccine, are permitted.

Contraception

Females of childbearing potential who are sexually active with a nonsterilised male partner must use at least 1 highly effective method of contraception (Table 1) from the time of screening, and must agree to continue using such precautions at least 90 days following the last infusion of durvalumab and avoid pregnancy for 9 months after RAI (¹³¹I) administration; cessation of birth control after this point should be discussed with a responsible physician. Periodic abstinence, the rhythm method, and the withdrawal method are not acceptable methods of birth control.

1. Females of childbearing potential are defined as those who are not surgically sterile (i.e., bilateral tubal ligation, bilateral oophorectomy, or complete hysterectomy) or postmenopausal (defined as 12 months with no menses without an alternative medical cause).
2. Subjects must use 2 acceptable methods of effective contraception as described in Table 1.

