Fixed archival and/or research biopsy tissues may also be evaluated by immunohistochemistry to assess changes in tumor immune infiltrates and tumor/immune cell protein expression (e.g. PD-L1 status). For patients in whom sufficient fresh tissue can be collected in the research biopsies, the tumor immune cell infiltrate (or tumor infiltrating lymphocytes ("TILs") may be extracted and characterized by cytometric techniques, including flow cytometry or mass cytometry (CyTOF).

Note regarding next generation sequencing analysis performed on this protocol: In the course of this research it is possible that some patients whose tumors are analyzed through investigational "next-generation" profiling in a research (non-CLIA) environment will be found to have somatic or germline mutations in genes that are known to be associated with an increased risk of cancer or other diseases. It will be stated in the consent that the participants will not receive any specific results from research tests. The consent will tell participants that if they wish to have genetic testing done for personal reasons than they should make an appointment with the MSK Clinical Genetics Service.

If in the course of this research a research finding is obtained that, in the opinion of the investigator, may be critical to the preventive care of the participant or their family, the investigator can communicate that finding to the IRB Genomic Advisory Panel (GAP). The finding will be reviewed by the GAP to determine whether the incidental finding should be discussed with the participant. For MSK, in the event that the GAP determines that the finding should be discussed with the participant, and the participant has consented to be re-contacted, then the

treating/consenting physician shall be contacted by the panel and asked to refer the participant to the Clinical Genetics Service for further discussion of the research finding.

The following information must be provided to GAP for review:

- Participant Name/MRN #
- Type of Biospecimen (tissue, blood, saliva)
- Incidental Finding
- Collection Protocol #
- Contact: [contact]

Peripheral Blood Analysis:

Exploratory Objective #1: To investigate changes in peripheral blood populations that occur with durvalumab and rhTSH-prepared RAI.

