Mutation burden, neoantigen landscape, and immunoediting analysis: While the low DTC mutation burden implies a low likelihood of neoantigen formation, neoantigen analysis has never been conducted for DTC. Whole-exome sequencing data will be analyzed using the neoepitope bioinformatics pipeline developed by [name] group. Mutation calling is performed by analyzing FASTQ files with four mutation callers and filtering by allelic frequency, call quality and other empiric measures. Mutations are validated with an orthogonal next-gen sequencing panel. Candidate neoantigens are identified based on peptide sequences and predicted binding to patient-specific MHC Class I alleles. RNAseq data will be used to define a set of expressed neoepitopes and explore gene expression signatures that may correlate with response. Evolution of the mutation, neoantigen, and gene expression landscape in pre- and post-treatment samples will be analyzed to gain insights into immunoediting that may occur and infer what epitopes may be critical for efficacy. RNAseq data will also be used to explore changes in the expression of nonmutated thyroid gene expression (TG, THSR, TPO, etc...) with therapy for the same purpose. *Biostatistical analysis:* Categorical pre- and post-treatment measures will be summarized by 2-by-2 tables; continuous pre- and post-treatment measures will be summarized by mean and standard deviation of the change as well as graphical method.

Immune cell infiltrate and immunologic gene signature analysis: Tumor RNAseq data will be used to analyze changes in (a) immune cell infiltration and (b) immunologic gene signatures with therapy. First, we will estimate the relative infiltration levels of individual immune cell populations in tumor samples using two computational approaches. The first was developed by [name] and [name] at MSK which uses single set enrichment analysis (ssGSEA) to determine the abundance of T cell and other immune cell populations in the tumor microenvironment³². A related but alternative approach uses support vector regression to model cellular populations based on a reference expression matrix³³. These techniques provide efficient and accurate alternatives to flow cytometry sorting. In addition, RNAseq data permits quantification of related immunologic gene expression signatures such as IFNy signaling, granzyme B, and antigen presenting machinery genes.

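### The T-cell subset analysis should report within-patient change from baseline, because per-visit summaries can move when the patients contributing samples change (minor, exploratory)

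*Combined protocol and SAP*

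**What the plan says.** The aim concerns change. Section 9.5 gives the blood objective as "To investigate changes in peripheral blood populations that occur with durvalumab and rhTSH-prepared RAI", and Section 14.0 says that "peripheral blood samples will be collected serially for flow cytometry to evaluate changes in T cell subsets at different time points of therapy".

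The method in Section 14.0 is a single sentence: "Proportions of T cell subsets will be summarized at each time point and plotted to reveal any trend". It specifies no change score, pairing with baseline, patient set or handling of missing samples.

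For continuous biopsy data the same section says that "continuous pre- and post-treatment measures will be summarized by mean and standard deviation of the change as well as graphical method". For cfDNA it plans to look at changes graphically.

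In Section 10.1, footnote o puts the first T-cell sample at Cycle 1 Week 1, before durvalumab. Under footnote p, later collection "will be conducted on Week 1 of Cycles 2, 3, and 4 (preferably prior to durvalumab administration, if possible), as well as Off Study". Footnote l ties the off-study evaluation to the last durvalumab dose (within 30 days of it), not to a fixed study week.

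**The concern.** The trial has 11 patients and no control arm, so each patient's own baseline is the only comparator for a treatment effect on blood T cells. A set of separate summaries at Cycle 1, 2, 3 and 4 does not use that comparator unless the same patients contribute at every visit. Treatment ends at confirmed progression, unacceptable toxicity or withdrawal, so some patients may give a baseline sample and no Cycle 4 sample. If their T-cell proportions tend to be higher or lower than those of the patients who stay, the plotted mean rises or falls through the change in membership alone. A real change in the remaining patients can be cancelled in the same way.

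The Off Study sample does not repair this. It falls at a different time in each patient, and in some it will coincide with progression. Placed at the end of the same series, it would mix time on treatment with reason for leaving.

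At stake is how one exploratory figure or table is read. No decision rule depends on it.

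**Working it through.** The plan states no figure for this analysis, so there is none to reproduce.

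**Inputs from the documents**
- 11 patients (Section 14.0).
- T-cell samples at about weeks 0, 4, 8 and 12 (Week 1 of Cycles 1 to 4 with four-week cycles), plus Off Study (Section 10.1, footnotes o and p).
- First on-treatment scan at week 8 ± 1 (Section 10.1).
- 12-month PFS of 36% in the pembrolizumab cohort described in Section 3.0.

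**Assumptions**
- The 36% applies to this trial, with a constant hazard.
- D, the difference in T-cell proportion between patients who stay and patients who leave. The documents give no value and show no link between T-cell level and leaving.

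**Step 1: expected progressions before the Cycle 4 sample.** With a constant hazard, the fraction progressed by week w is 1 − S^(w/52), where S is 12-month PFS.

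| 12-month PFS | By week 8 | of 11 | By week 12 | of 11 |
|---|---|---|---|---|
| 36% | 1 − 0.36^(8/52) = 14.5% | 1.6 | 1 − 0.36^(12/52) = 21.0% | 2.3 |
| 50% (range) | 10.1% | 1.1 | 14.8% | 1.6 |
| 20% (range) | 21.9% | 2.4 | 31.0% | 3.4 |

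The week 8 column is what the first scheduled scan could detect. The week 12 column also counts later progression, which scheduled imaging would not normally pick up before the next scan. These are progressions, not lost samples.

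**Step 2: shift in the per-visit mean.** If k of 11 leave and nobody changes, the mean of those who stay minus the mean of all 11 is (k/11) × D, where D is the stayers' level minus the leavers' level.
- k = 2, D = 10: 2/11 × 10 = 1.8 points.
- False rise: nine patients at 40% and two at 30% have a mean of (9 × 40 + 2 × 30)/11 = 38.2%. Without the two, the mean is 40.0%.
- Hidden rise: nine at 40% and two at 50% have a mean of (9 × 40 + 2 × 50)/11 = 41.8%. If the two leave and each of the nine rises by 1.8 points, the mean is still 41.8%.
- For k from 1 to 4 and D from 5 to 15, the shift runs from 1/11 × 5 = 0.5 to 4/11 × 15 = 5.5 points.

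**Step 3: does pairing help?** A simulation of 40,000 trials of 11 patients assumed no true change, an SD of 10 points, a within-patient correlation of 0.8, and leaving more likely at low levels (log-odds slope 0.5 to 1.5 per SD of a patient's stable level).

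| Loss | Bias, per-visit means | Bias, mean within-patient change |
|---|---|---|
| 21% | +0.9 to +2.1 | 0.0 |
| 36% | +1.5 to +3.5 | 0.0 |

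At 21% loss the sampling SD is about 2.2 for the paired change, against about 2.6 for the difference in per-visit means. When leaving is unrelated to level, both methods are unbiased. The simulation did not make leaving depend on the change itself; pairing would not remove that bias.

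**The case against.** The strongest reply is that Section 14.0 is under-specified here, not wrong. It defines no patient set, so summarising only the samples available at each visit is an inference, although the natural one. With 11 patients, plotting may well mean one line per patient, which would show within-patient change directly. Both points stand, and they are why this is a matter of clarification.

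A reader might also infer a progressively more selected group across Cycles 2, 3 and 4. The schedule does not support that. The Cycle 2 and 3 samples come before or around the first scan, so loss to radiographic progression falls mainly on the Cycle 4 sample. Stopping requires confirmed progression, and Section 13.1 allows treatment beyond it, so a patient who progresses at week 8 may still give a Cycle 4 sample. The replacement rule in Section 9.4 covers those who do not complete six weeks for reasons other than DLT, though the plan does not say whether their baseline samples count.

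The biopsy comparison is imperfect, because those data have two time points and the blood series has up to five. It still shows that the section uses change scores where change is the question.

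Finally, it may be tempting to treat draws after infusion and steroid exposure as established biases, since footnote p only prefers pre-dose draws and Section 9.2 says that "A temporary period of steroids will be allowed for different indications". No document shows that either shifts T-cell proportions, so neither supports a change to the sampling rule.

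**Conclusion.** The point holds as a minor, free improvement. The stated aim is change, the stated method is a per-visit summary, and a paired summary matches the aim better at almost no cost. Under the assumed 36% 12-month PFS and constant hazard, about 1.6 to 2.3 of 11 patients would have progressed before Cycle 4. With two leavers and an assumed 10-point difference, the artificial shift is about 1.8 points. The formula (k/11) × D is exact; the values of k and D are assumptions, and there is no shift if leaving is unrelated to T-cell level.

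A reader might infer that the trial's evidence for its immune hypothesis is compromised. The documents do not support this. The T-cell summary is exploratory and descriptive, with no test and no decision attached. It sits beside serial biopsies, T-cell receptor analysis, ex vivo assays, cfDNA and thyroid antibody serologies. The DLT rule, BOR and PFS are unaffected.

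**What to change.** In Section 14.0, replace the T-cell summary sentence with text to this effect:

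*For each T-cell subset, within-patient change from the Cycle 1 Week 1 sample will be summarised by its mean and SD at Cycles 2, 3 and 4 among patients with both samples, with the number of pairs shown at each visit. Individual patient lines will be plotted. The Off Study sample will be presented separately because its timing differs between patients. Paired change does not remove bias from dropout that is related to the change itself.*

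Optionally, and without altering the sampling rule, record whether each Cycle 2 to 4 sample was drawn before or after that day's infusion and whether the patient was then taking systemic steroids. Concurrent medications are already recorded at these visits, so the steroid item needs no new collection.

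The cost is analysis wording and, if the option is taken, one or two data items. No new samples, visits or patients are needed.
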